8.3.1.1 Concomitant Temozolomide, if Radiotherapy Is Interrupted

If radiotherapy has to be temporarily or permanently interrupted for technical or medical reasons unrelated to the TMZ administration, then treatment with daily TMZ should continue.

8.3.2 Post-Radiation (Adjuvant) Temozolomide

Continued dosing administration is based on adverse events (AEs) during the prior treatment cycle. If multiple AEs are seen, the dose administered should be based on the dose reduction required for the most severe grade of any single AE.

Dose Level	Temozolomide Dose, mg/m ² /day	Remarks
-1	100	Reduction if prior AE
0	150	Starting dose cycle 1 (adjuvant)
+1	200	Escalated dose at cycle 2, for cycles 2 – 12 in absence of AE

Delay

On Day 1 of each cycle (within the prior 72 hours), ANC $\geq 1.5 \times 10^9/L$, platelet count $\geq 100 \times 10^9/L$ and all treatment-related grade 3 or 4 non-hematologic AEs (except alopecia, nausea, and vomiting) must have resolved (to grade ≤ 1).

If AEs persist, treatment should be delayed by 2 weeks for up to 4 consecutive weeks, so that the TMZ dosing can coincide with the administration of the ABT-414 or placebo. If, after 4 weeks of delay, all AEs have still not resolved, then any further adjuvant treatment with TMZ should be stopped. When possible, TMZ treatment when resumed should start on either Day 1 or Day 15 of a cycle so that it may coincide with ABT-414/placebo treatment.

Dose Escalation

If, during the first cycle, all non-hematologic AEs observed were grade ≤ 2 (except alopecia, nausea and vomiting) and with platelets $\geq 100 \times 10^9/L$ and ANC $\geq 1.5 \times 10^9/L$, then the TMZ dose should be escalated to dose level 1 and this dose should be used as the starting dose for subsequent cycles. If treatment after cycle 1 has to be delayed because of ongoing non-hematologic AEs of grade ≥ 2 , then no escalation is possible. If the dose was not escalated at cycle 2, then the dose should not be escalated in further cycles (Cycles 3 – 6).

Dose Reductions

If any non-hematologic AE observed was grade > 2 (except alopecia, nausea and vomiting) and/or if platelets $< 50 \times 10^9/L$ and/or ANC $< 1 \times 10^9/L$, then the dose should be reduced by one dose level. For subjects who would require dose reductions to a dose level $< 100 \text{ mg/m}^2/\text{day}$, TMZ will be stopped. Also, if any of the same non-hematologic grade 3 AE recurs (except alopecia, nausea and vomiting) after reduction for that AE, then TMZ will be stopped.

If any treatment-related non-hematologic AE observed was grade 4 (except alopecia, nausea and vomiting) then adjuvant TMZ treatment should be stopped.

Subsequent cycles (Cycles 3 – 12): Any dose reductions of TMZ will be determined according to (1) non-hematologic AE during the preceding treatment cycle, as well as (2) the nadir (lowest/worst) ANC and platelet counts observed. No dose escalation should be attempted. The same dose reductions as for the second cycle should be applied.

Important: If the dose was reduced or delayed for adverse events, there will be no dose escalation.

The reason(s) for dose reduction and/or delay must be documented in the eCRF.

Summary of Dose Modification or Discontinuation During Post-Radiation Temozolomide

Worst Non-Hematologic AE (Except Alopecia, Nausea and Vomiting) During the Previous Cycles	
Grade	Dose Modification
0 – 2	No dose modifications for non-hematologic AEs. Dose escalations (only for cycle 2) or reductions based on ANC and platelet counts are applicable.
3	Reduce by one dose level (except alopecia, nausea and vomiting). Dose modifications (escalations or reductions) based on ANC and platelet counts are not applicable. No further escalation is possible. If the same non-hematologic grade 3 AE recurs (except alopecia, nausea and vomiting) after reduction for that AE, then stop temozolomide.
4	Stop temozolomide (except for alopecia, nausea and vomiting). Dose modifications (escalations or reductions) based on ANC and platelet counts are not applicable.

Nadir Values

ANC	Action
$\geq 1.5 \times 10^9/L$	Escalation to DL 1 (cycle 2 only)
$\geq 1 \text{ \& } < 1.5 \times 10^9/L$	Dose unchanged
$< 1 \times 10^9/L$	Reduce by 1 dose level
Platelets	
$\geq 100 \times 10^9/L$	Escalation to DL 1 (cycle 2 only)
$50 - 99 \times 10^9/L$	Dose unchanged
$< 50 \times 10^9/L$	Reduce by 1 dose level

Note: A complete blood count must be performed on Day 22 (+/- 3 days) of each adjuvant treatment cycle.

Hematologic AE on Day 1 of Each Cycle (Within 72 Hours Before)

AE	Delay
ANC $< 1.5 \times 10^9/L$ and/or Platelet count $< 100 \times 10^9/L$	Delay up to 4 weeks until all resolved. If unresolved after 4 weeks then stop temozolomide. If resolved, dose delay/reductions based on non-hematologic AEs are applicable. If treatment has to be delayed for AEs, then no escalation is possible.

Non-Hematological AE (Except for Alopecia, Nausea and Vomiting) on Day 1 of Each Cycle (Within 72 Hours Before)

Grade	Delay
2 – 3	Delay up to 4 weeks until all resolved (to grade ≤ 1). If unresolved after 4 weeks, then stop temozolomide. If resolved, dose delay/reductions based on ANC and platelets are applicable. If treatment has to be delayed for AEs, then no escalation is possible.

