Subjects in Arm A will receive ABT-414 on Day 1 and Day 15 of each 28-day cycle. Subjects in Arm B will receive placebo IV infusion on Day 1 and Day 15 of each 28-day cycle. Subjects who discontinue TMZ for TMZ-related toxicity will continue ABT-414/placebo treatment. Subjects who discontinue ABT-414 or placebo due to ABT-414-related or placebo-related

toxicity prior to completion of the Adjuvant Therapy Phase will continue TMZ treatment as scheduled.

Duration of Adjuvant ABT-414 or Placebo

If after completing 12 cycles of adjuvant ABT-414/placebo, the subject is tolerating treatment and the Investigator believes the subject is continuing to benefit from ongoing study drug treatment, the Investigator may extend the Adjuvant Phase with ABT-414/placebo after consultation with the Neuro-Medical Oncology Chair or AbbVie Medical Monitor. The ABT-414/placebo will continue at the same dosing schedule, as long as disease progression has not been determined.

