Dose reductions or delays should be made for the likely causative agent. If one of the agents should be stopped for any reason other than disease progression, the subject can continue on the other single agent alone at the same dose and schedule.

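### Adjuvant temozolomide dose rules in Protocol 8.3.2 act on any non-hematologic AE, in conflict with 8.0, 5.3.1.2 and their own prose, and the SAP does not report adjuvant TMZ dose by arm

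*Protocol*

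**What the plan says.** Section 8.0 of the protocol sets the general principle: "Dose reductions or delays should be made for the likely causative agent". If one agent is stopped for a reason other than progression, "the subject can continue on the other single agent alone at the same dose and schedule". Section 5.1 adds that subjects who discontinue ABT-414 or placebo for its own "toxicity prior to completion of the Adjuvant Therapy Phase will continue TMZ treatment as scheduled".

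Section 8.3.2 then gives the adjuvant TMZ rules:

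- **Reduction prose:** "If any non-hematologic AE observed was grade > 2 (except alopecia, nausea and vomiting" are the only exceptions), or if counts are low, go down one level. TMZ stops if the same Grade 3 event recurs after a reduction. Neither rule mentions cause.
- **Summary table, Grade 3 row:** "Reduce by one dose level (except alopecia, nausea and vomiting" again being the only exceptions). The Grade 4 row stops TMZ, also without mention of cause, although the Grade 4 prose requires a treatment-related event.
- **Escalation prose:** escalation at cycle 2 requires that all non-hematologic AEs stayed at Grade 2 or below, whatever their cause. Section 5.3.1.2 lets only treatment-related AEs above Grade 2 block it.
- **Delay prose:** on Day 1, "all treatment-related grade 3 or 4 non-hematologic AEs (except alopecia, nausea, and vomiting) must have resolved" to Grade 1 or below.
- **Day 1 table, row for Grades 2 to 3 of any cause:** "Delay up to 4 weeks until all resolved (to grade ≤ 1). If unresolved after 4 weeks, then stop temozolomide". The escalation paragraph also expects delay from Grade 2: "If treatment after cycle 1 has to be delayed because of ongoing non-hematologic AEs of grade" 2 or higher, escalation is lost.

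For TMZ during radiation, the 8.3.1 prose limits the non-hematologic triggers to AEs possibly related to TMZ. The 8.3.1 summary table drops that limit.

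For adjuvant TMZ, SAP 9.2 plans the number of cycles and treatment duration. It plans cumulative TMZ dose only for chemoradiation, and in mg/kg.

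**The concern.** The trial tests ABT-414 added to a fixed RT/TMZ backbone. ABT-414 has a characteristic non-hematologic toxicity, corneal epitheliopathy, and eye events are not among the exceptions in 8.3.2. For one eye event attributed only to ABT-414, the protocol therefore states two actions: leave TMZ alone (8.0) or change it (8.3.2).

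The literal reading treats the backbone more strictly than the drug causing the event. For Grade 3 eye toxicity, Table 10 in 8.1.2.4 recommends but does not require interrupting or reducing ABT-414, whereas 8.3.2 says the TMZ dose should come down. Section 5.12.4 says the corneal changes usually reverse 4 to 6 weeks after ABT-414 is withheld, whereas the Day 1 table stops TMZ if an event has not settled within 4 weeks.

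If sites follow 8.3.2 to the letter, TMZ falls mainly in the ABT-414 arm, and the comparison becomes ABT-414 plus less TMZ against full TMZ. The planned exposure table would not show the dose that each arm received.

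**Working it through.** **Step 1. Rules side by side**

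| Event | One instruction | Conflicting instruction |
|---|---|---|
| Grade 3 eye AE attributed only to ABT-414 | 8.0: act on the causative agent, so no TMZ reduction | 8.3.2 reduction prose and Grade 3 row: TMZ down one level |
| Grade 2 or 3 eye AE attributed only to ABT-414, ongoing on Day 1 | 8.0: no TMZ delay | Day 1 table: delay TMZ up to 4 weeks, then stop |
| Grade 3 AE in cycle 1, unrelated to any treatment | 5.3.1.2: escalation allowed | 8.3.2 escalation prose: no escalation |
| Grade 4 AE, unrelated to any treatment | 8.3.2 prose: above Grade 2, so one level down | Summary table: stop TMZ |
| AE ongoing at Grade 2 on Day 1 that never exceeded Grade 2 | Delay prose: no delay | Day 1 table: delay, and escalation is lost |

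The Delay prose and the Day 1 table agree on grade for an AE that reached Grade 3 and has improved only to Grade 2: both delay. Their grade conflict is confined to the last row.

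Treatment-related is not specific to TMZ. Section 7.3 defines protocol treatment as ABT-414/placebo, TMZ and radiation, with a separate causality assessment for each. Copying the 5.3.1.2 wording into 8.3.2 would therefore still let an ABT-414 eye event hold TMZ back.

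**Step 2. Per-patient dose under literal use**

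Inputs: 5 dosing days per cycle; 150 mg/m²/day in cycle 1 and 200 in cycles 2 to 6 (5.3.1.2); dose levels 100, 150 and 200 (8.3.2). Cycle dose = daily dose × 5, giving 500, 750 or 1,000 mg/m².

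Planned: 750 + 5 × 1,000 = 5,750 mg/m².

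| First trigger | Total over 6 cycles (mg/m²) | Change |
|---|---|---|
| Grade 3 in cycle 1 (no escalation, then one level down) | 750 + 5 × 500 = 3,250 | −43.5% |
| Grade 3 in cycle 2 | 750 + 1,000 + 4 × 750 = 4,750 | −17.4% |
| Grade 3 in cycle 3 | 750 + 2 × 1,000 + 3 × 750 = 5,000 | −13.0% |
| Grade 3 in cycle 4 | 750 + 3 × 1,000 + 2 × 750 = 5,250 | −8.7% |
| Grade 3 in cycle 5 | 750 + 4 × 1,000 + 750 = 5,500 | −4.3% |
| Escalation barred only | 6 × 750 = 4,500 | −21.7% |

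Delays, recurrence stops and optional cycles 7 to 12 are left out.

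**Step 3. How unequal the trigger could be**

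The interim summary in protocol Section 1.0 gives Grade 3 or higher corneal AEs in 61.0% and 0.6% of subjects, a gap of 60.4 points. For any Grade 3 or higher AE the figures are 87.3% and 62.3%, a gap of 25.0 points. The second gap is smaller because many placebo subjects also have a high-grade AE, and a non-hematologic one would trigger the same rule. Both gaps cover the whole study, and the second includes hematologic AEs, so neither is the adjuvant-phase trigger rate. Grade 2 rates by arm are not given.

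**Step 4. What rewording can still reach**

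SAP 6.0 has the last main-study subject enrolled by 19 March 2018. Assuming treatment from that date without delays, 6 or 7 weeks of radiation plus 4 weeks puts adjuvant Cycle 1 Day 1 on 28 May or 4 June 2018. Adding 20 weeks and 4 days ends cycle 6 TMZ on 19 or 26 October 2018. Adding 44 weeks and 4 days instead ends optional cycle 12 TMZ on 5 or 12 April 2019, before the interim data cut of 30 April 2019.

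**The case against.** The best defence is that silence on cause has a default. Section 8.3.2 sits under 8.0, and the protocol says so explicitly when it wants action whatever the cause, as in Table 11 of 8.1.6 and in 8.4. Eye toxicity has its own table, which changes only ABT-414/placebo. A careful site could reach the sensible answer this way, so sites are not forced to cut TMZ. The default is weak, however. Section 8.3.2 requires treatment-relatedness in two of its rules and writes any or all in others, and the 8.3.1 prose names TMZ, so a reader can take the difference as intended. The discretion in 8.3 does not settle it, because it covers only conflict with local prescribing information.

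Several stronger readings are tempting, and the documents do not support them:

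- **That all of 8.3.2 contradicts 8.0.** The causative-agent sentence covers reductions and delays, not escalation or stopping. The sentence on continuing the other agent applies once one agent is stopped, and the 5.1 text applies once ABT-414/placebo is discontinued.
- **That Day 1 delay has two wholly different thresholds.** The prose can be read as the grade an AE reached and the table as its grade on Day 1. Only the never-above-Grade-2 case then remains in conflict on grade.
- **That the SAP would miss eye-driven TMZ changes.** Corneal epitheliopathy is an AE of special interest, and the 11.2.1 overview is repeated for each such AE. With 11.2.2, AE-driven TMZ reductions, interruptions and discontinuations are tabulated by arm. Only withheld escalation and the dose received are missing.
- **That TMZ was in fact lower in the ABT-414 arm, or that this explains the interim OS hazard ratio of 1.01.** The documents report no TMZ dose by arm and do not say how sites applied the rules.

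The limited reach of rewording also stands. Appendix X plans TMZ for 6 cycles only, discontinues placebo subjects and leaves ocular management to the investigator. The Chinese cohort was still enrolling at the SAP date, but no later count on TMZ is given.

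**Conclusion.** The conflict is real and narrower than it first looks. The one-level reduction rule, the Grade 3 row and the Day 1 table conflict with 8.0. The escalation rule conflicts with 5.3.1.2, and the Grade 4 row with the Grade 4 prose. The Delay prose and the Day 1 table differ on grade only for an AE that never exceeded Grade 2. This is an incorrectly stated rule, not a missing detail.

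The per-patient losses in Step 2 hold only if 8.3.2 is applied literally. The direction, less TMZ mainly in the ABT-414 arm, rests on the corneal imbalance. The size at arm level is unknown, and no effect on OS is shown. Because main-study TMZ was essentially complete by the interim cut, what remains useful for the OS comparison is to show whether backbone TMZ was balanced.

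**What to change.** 1. **Cause.** In 8.3.2, limit the escalation, reduction, recurrence-stop, Grade 4 and delay rules, and the matching table rows, to AEs judged possibly related to TMZ, as the 8.3.1 prose does. Align 5.3.1.2 and the non-hematologic rows of the 8.3.1 summary table.
2. **Day 1 threshold.** State one threshold in the Delay prose, the Escalation prose and the Day 1 table, and say whether an AE that never exceeded Grade 2 delays TMZ.
3. **SAP 9.2.** Report by arm the adjuvant cumulative TMZ dose or relative dose intensity in mg/m², and the proportion escalated to 200 mg/m². Relative dose intensity over cycles started is preferable, because cumulative dose also reflects time to progression. Change the TMZ unit in the chemoradiation row from mg/kg to mg/m².

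Item 3 costs a few rows and one unit. Exact TMZ doses and reasons for reduction or delay already go into the eCRF, and height and weight are collected. No new AE table is needed. Items 1 and 2 are wording only and use the causality already recorded for each component, but an amendment needs ethics approval (15.1) across approximately 200 sites. They can affect only subjects still on TMZ, who are few if any in the main study. If no further amendment is planned, item 3 is the one to keep.

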8.4 Hepatic Laboratory Abnormalities

This section provides information on safety monitoring, evaluation of potential causes, and appropriate documentation for subjects with hepatic laboratory abnormalities suggesting potential drug-induced liver injury (DILI). It was adapted with modifications from the FDA Guidance for Industry, Drug-Induced Liver Injury: Premarketing Clinical Evaluation (<https://www.fda.gov/downloads/Drugs/GuidanceComplianceRegulatoryInformation/Guidances/UCM174090.pdf>) in consultation with a hepatologist with expertise in DILI.

Information derived from the scientific literature and public databases on liver injury attributable to prescription and nonprescription medications, herbals and dietary supplements can be found at the LiverTox database (<https://livertox.nlm.nih.gov>).

If a subject develops one of the following laboratory abnormalities, hepatic laboratory abnormalities should be confirmed by repeat testing, and the subject should be monitored and evaluated as described in this section, **regardless of the assessed relationship to the study treatments:**

- ALT or AST $> 3 \times$ ULN **and** TBL $> 2 \times$ ULN, or
- ALT or AST $> 5 \times$ ULN (or $> 5 \times$ the baseline value if elevated) or $> 8 \times$ ULN, whichever is lower

Confirmation of Liver Test Abnormalities

For subjects meeting either of the criteria above, confirmation of hepatic laboratory abnormalities should be done as follows:

- **Repeat testing of all four of the usual measures (ALT, AST, alkaline phosphatase, and TBL) should be performed within 3 days of the initial abnormality** to confirm the abnormalities and to determine if they are increasing or decreasing.
 - Serum transaminases may rise and fall quite rapidly, and waiting a week or two before obtaining confirmation of elevations may lead to a false conclusion that the initially observed abnormality was spurious.
 - The need for prompt repeat testing is especially great if AST or ALT is $> 3 \times$ ULN **and** TBL $> 2 \times$ ULN.
 - If the subject is unable to return to the trial site promptly, the subject should be retested locally, with results and normal laboratory ranges recorded in the CRFs.

- **Inquire about concurrent new or escalating symptoms** (e.g., right upper quadrant pain or tenderness, fever, rash). Although non-specific in the setting of GBM treatment, fatigue nausea, and vomiting should also be assessed as clinical symptoms potentially associated with liver injury.

It is appropriate to initiate *close observation* (described below) to determine whether the abnormalities are improving or worsening and to consider whether the subject meets criteria for stopping study drug if symptoms suggestive of liver injury persist or if repeat testing shows:

- ALT or AST $> 5 \times$ ULN (or $> 5 \times$ baseline if elevated or $> 8 \times$ ULN, whichever is lower) or
- ALT/AST $> 3 \times$ ULN **and** total bilirubin $> 2 \times$ ULN.

Close Observation

It is critical to initiate close observation immediately upon detection and confirmation of early signals of possible DILI (as described above), and not to wait until the next scheduled visit or monitoring interval. The primary goal of close observation is to determine as quickly as possible whether observed abnormal findings are transient and will resolve spontaneously or will progress to marked serum aminotransferase elevation or evidence of *functional* impairment, as indicated by rising bilirubin or INR, which represent substantial liver injury.

Close observation includes:

- **Repeating liver enzyme and serum bilirubin tests two or three times weekly. If total bilirubin is elevated, obtain direct bilirubin.** Frequency of retesting can decrease to once a week or less if abnormalities stabilize or drug has been discontinued and the subject is asymptomatic.
- **Obtaining additional tests, as appropriate, to evaluate liver function, (e.g., international normalized ratio [INR]); diagnostic measures (e.g., ultrasound of the liver), serum ammonia, etc.**
- Obtaining a more detailed history of symptoms and prior or concurrent diseases. Update the appropriate eCRFs (if applicable).
- Obtaining a history of concomitant drug use (including nonprescription medications and herbal and dietary supplement preparations), alcohol use, recreational drug use, and special diets. Update the appropriate eCRFs (if applicable).
- Ruling out other immediately apparent possible causes of aminotransferase (ALT or AST) elevation and hyperbilirubinemia, as described below.

- Obtaining a history of exposure to environmental chemical agents.
- Considering gastroenterology or hepatology consultations.

Relevant supplemental information must be collected and entered in the appropriate eCRF(s),

Evaluating Data for Alternative Causes

An important purpose of close observation is to gather additional clinical information to seek other possible causes of the observed liver test abnormalities, such as one of the following common causes:

- **Acute viral hepatitis.** The usual onset of hepatocellular DILI is indistinguishable from acute viral hepatitis A or B. Hepatitis C is much less often acute in its onset and tends to be insidious, but it sometimes can resemble acute DILI. The presence of acute viral hepatitis A, B, and C should be evaluated by serological markers. Viral hepatitis D (requires concomitant hepatitis B infection) and E are relatively rare in the United States. Hepatitis E is more common in developing countries, including Southeast Asia, and should be considered in recent travelers to those countries and in patients in trials conducted in those countries. Also rare are hepatocellular liver injuries caused by Epstein-Barr virus, cytomegalovirus, herpes simplex virus, toxoplasmosis, varicella, and parvovirus, although these infections are seen more typically in immuno-suppressed individuals. Adolescent and young adult patients with possible DILI should be tested for Epstein-Barr virus. Hepatitis is common among transplant patients with cytomegalovirus disease.
- **Alcoholic and autoimmune hepatitis.** Acute alcoholic hepatitis usually is recurrent, with a history of binge exposure to alcohol preceding episodes, and it has some characteristic features, such as associated fever, leukocytosis, right upper quadrant pain and tenderness, hepatomegaly, and AST > ALT, that may help distinguish it from other causes of liver injury. Other features of the physical examination may include the presence of stigmata of cirrhosis, such as spider nevi, palmar erythema, estrogenic changes in males, and Dupuytren's contractures. Alcoholic and autoimmune hepatitis should be assessed by history, physical examination, and laboratory testing, including serologic testing (e.g., antinuclear or other antibodies).
- **Hepatobiliary disorders.** Biliary tract disease, such as migration of gallstones or intrahepatic lesions, more often causes cholestatic injury initially and should be investigated with gall bladder and ductal imaging studies, especially if alkaline phosphatase is increased. Malignant interruption of the biliary tract also should be considered.
- **NASH.** NASH may be seen in obese, hyperlipoproteinemic, and/or diabetic patients and may be associated with fluctuating aminotransferase levels, and hepatic and

sometimes splenic enlargement. It is sometimes associated with cirrhosis and portal hypertension.

- **Cardiovascular causes.** Cardiovascular disease, especially right heart failure and hypotension or any cause of impaired oxygenation of the liver, may cause acute centrilobular hypoxic cell necrosis (ischemic hepatitis) with rapid and sometimes spectacular increases of serum transaminases (e.g., ALT or AST > 10,000 U/L). Cardiovascular dysfunction or impaired liver oxygenation, including hypotension or right heart failure, should be assessed by physical examination and history.
- **Concomitant treatments.** It is critical to discover concomitant treatments, including exposure to nonprescription and dietary supplement products that might be responsible for injury. The possible exposure to potentially toxic herbal or dietary supplement mixtures (sometimes of unknown composition), nonprescription medications such as acetaminophen, or to occupational chemical agents may not be volunteered unless subjects are specifically questioned.

Follow-Up to Resolution

All subjects showing hepatic laboratory abnormalities suggestive of possible DILI should be followed until satisfactory resolution of the laboratory abnormalities). DILI may develop or progress even after the causative drug has been stopped. Local lab results should be recorded on appropriate eCRFs.

Dose Modifications for Study Drugs

See the dose modification guidelines for each respective drug.

